Safety, tolerability, and pharmacokinetics of an oral *Withania somnifera* product in older adults

NCT06171724

Version Date: 10.10.2024

Title: Safety, tolerability, and pharmacokinetics of an oral *Withania somnifera* product in older adults

Principal Investigator: [name], ND, MS [contact]

Co-Investigators/staff: [name] (Clinical Investigator) [contact]
[name] (Co-Investigator) [contact]
[name] (Study staff)
[name] (Study staff)

A. OBJECTIVES

A.1. Purpose

The purpose of this pilot study is to measure the oral absorption and pharmacokinetics (PK) of compounds from two doses of a standardized *Withania somnifera* extract product (Shoden®) in healthy older adults. Compound levels will be measured in human plasma and urine over 48 hours after acute oral administration and after four weeks' use of Shoden®. Peak exposure and time, total exposure, half-life, and urinary excretion of compounds will be calculated. These data will be used to inform decisions on the dosage and dosing frequency for future phase 1 and phase 2 clinical trials.

A.2. Primary goal

To determine the oral bioavailability and PK of withanolides from two doses of a *Withania somnifera* product (Shoden®) in healthy older adults following single administration and after four weeks' use.

A.3. Endpoints

- Primary endpoints:
 - Peak exposure and time (C_{max} , T_{max}) and total exposure (AUC_{0-t} , $AUC_{0-\infty}$) of withanolides from Shoden® in human plasma after a single administration.
- Secondary endpoints:
 - Half-life ($t_{1/2}$) of withanolides from Shoden® to help determine dosage intervals.
 - Urinary excretion of withanolides from Shoden®
 - Steady-state levels of withanolides after four weeks' use.
 - Tolerability and safety of Shoden® following single administration and after four weeks' use.
 - Feasibility of assessing sleep- and stress-related outcomes remotely using REDCap surveys.

B. SPECIFIC AIMS

Aim 1: Evaluate the oral absorption and PK of selected withanolides from Shoden® in older adults.

- **Hypothesis:** Selected withanolides will be detectable in the plasma and urine at both doses of Shoden®, with significantly greater plasma levels achieved at the 480 mg dose.

Aim 2: Assess the safety and tolerability of Shoden® in older adults.

- **Hypothesis:** A single administration and four weeks' use of Shoden® at 240 and 480 mg per day will be well tolerated and produce no severe adverse events.

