In animals, WS extracts have also been shown to be safe in toxicity studies. Acute and sub-acute toxicity of a hydroalcoholic root extract of WS was investigated in female Wistar rats.⁴⁴ No behavioral signs of toxicity or gross pathological changes were observed with acute doses up to 2000 mg/kg. Similarly, no signs of subacute toxicity were observed in rats given 500, 1000 or 2000 mg/kg of the extract daily for 28 days. In a separate study, a hydroalcoholic root extract of WS was used to assess prenatal developmental toxicity in rats at doses of 500, 1000 and 2000 mg/kg daily for 28 days.⁴⁵ No signs of toxicity, gross pathology changes, or mortality were observed in the pregnant rats or fetuses. Further studies are required to examine the safety of WS extracts prepared using other extraction methods and plant parts.

In humans, the widespread use of WS as a traditional medicine and dietary supplement, as well as current scientific literature, support its general safety. In a review of clinical trials that used root preparations of WS for a wide variety of conditions, the authors noted that reasonable safety outcomes were seen with no serious adverse events or changes in vital signs or hematological and biochemical parameters.⁴⁶ Mild to moderate transient adverse events including somnolence, giddiness, vertigo, drowsiness, and gastrointestinal effects (e.g., nausea, epigastric pain, loose stools, constipation, decreased appetite) were reported in some studies, while other studies involving adults and children did not report any adverse events.⁴⁶ Similarly, an earlier review reported that WS has been used in all age groups and in both sexes, even during pregnancy, without any reported side effects.¹⁰ One study formally measured the tolerability of a WS root extract using the Patient's Global Assessment of Tolerability to Therapy and found it to have a high tolerability score.⁴⁷ Rare, serious adverse events have been reported, however. Isolated cases of mild to severe liver toxicity have occurred, with three deaths in patients who had underlying liver disease.⁴⁸⁻⁵⁰ A case report has also been published detailing a kidney transplant rejection due to WS.⁵¹ Liver and renal abnormalities will be assessed at the beginning and end of each four-week study period.

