Study Title: Safety, tolerability, and pharmacokinetics of an oral *Withania somnifera* product in older adults

Principal Investigator: [name], ND, MS

IRB#: STUDY00026055

Version Date: 10.10.2024

F.2. Study Population

F.2.1. Number of participants

Twelve non-demented older volunteers (6 female, 6 male) 65 years of age or older will be screened and enrolled in the study. We estimate that we will need to screen approximately twenty potential participants to meet the twelve volunteers needed to complete the study. We expect two dropouts, for a total of 10 participants completing the study.

F.2.2. Inclusion and exclusion criteria

Inclusion criteria:

1. Age 65 and older, male and female
2. Body Mass Index (BMI) greater than 17 and less than 35 at screening
3. Sufficient vision and hearing to complete all tests
4. Willingness to discontinue all botanical supplementation for one week prior to and throughout study
5. No known sensitivity to *Withania somnifera* or any of its derivatives
6. Normal or clinically not significant 12-lead electrocardiogram (ECG) recording
7. Hepatic (ALT, AST, bilirubin), renal (creatinine, estimated GFR), and TSH parameters within normal range
8. Hemoglobin ≥ 13.0 g/dL or hematocrit $\geq 39\%$ (males) OR hemoglobin ≥ 12.5 g/dL or hematocrit $\geq 38\%$ (females), per FDA recommendations on blood donation
9. General health status that will not interfere with the ability to complete the study
10. Willingness to attend all study visits
11. Willingness to avoid caffeine and xanthine-containing foods or beverages (e.g., coffee, tea, chocolate, caffeine-containing sodas, colas, etc.), as well as grapefruit juice and poppy-containing foods for 48 hours prior to baseline visits
12. Willingness to adhere to special diet (no dairy, grapefruit products, poppy-containing foods, high-fat meals, caffeine, or xanthine-containing foods or beverages) during baseline visits and until after 24-hour visit
13. Mini-Mental State Exam (MMSE) score ≥ 27

Exclusion criteria:

1. Current smoking, alcohol, or substance abuse according to DSM-V criteria
2. Participants who are currently pregnant, actively trying to conceive a child, or planning to within three months of study completion
3. Severe aversion to venipuncture
4. Donation of blood within 90 days of screening
5. Participation in drug research study within 90 days of screening

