a 15-minute LC-MRM-MS method for the BENFRA Center for the analysis of seven withanolides using digoxin-d₃ as an internal standard (section E.3, Figure 2). The BENFRA center (through [name]) is working with the BSR/PKCore lab to include the four additional withanolides in the method and optimize mouse plasma work-up methods for the analysis. These methods will be adapted for human plasma and urine in this study, using commercially available human plasma and urine spiked with reference withanolides under the guidance of [name] and [name], director of the BSR/PKCore.

Each withanolide analyte will be identified by its retention time and characteristic mass spectral fragmentation pattern using selected reactions within a multiple-reaction monitoring paradigm. The peak area ratio to the appropriate internal standard will be identified and evaluated against the standard calibration curve of each analyte prepared by spiking known concentrations into blank plasma. Each analyte's concentration in participant plasma will be used to generate a concentration-time curve for pharmacokinetic profiling. The primary endpoints are the maximum concentration (C_{max}) and its corresponding timepoint (t_{max}) of each withanolide analyte. To determine the rate of elimination (k), linear regression of the plasma concentration against time will be used. This value will be used to determine the elimination half-life ($t_{1/2}$) using the formula $t_{1/2}=0.693/k$. Area under the concentration-time curve from dosing (time 0) to time t (AUC_{0-t}) will be calculated using the linear-log trapezoidal method. Area under the concentration-time curve from dosing (time 0) extrapolated to infinite time ($AUC_{0-\infty}$) will be calculated using the equation $AUC_{0-t} + AUC_{t-\infty}$, where $AUC_{t-\infty} = C_{last}/k_e$. C_{last} is the last observed concentration and k_e is the elimination rate constant. Differences in C_{max} , AUC_{0-t} , $AUC_{0-\infty}$, and $t_{1/2}$ for the two doses of Shoden® will be evaluated using paired t-tests or the non-parametric equivalent Wilcoxon paired test, while differences in t_{max} will be compared between dose groups using chi-square tests of distribution. With numerous analytes of interest, post-hoc multiple comparison adjustments in p-values will be applied using the Holm-Sidak stepwise correction. All final statistical tests will be two-tailed and considered significant at $\alpha=0.05$.

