Peak area for each withanolide analyte and internal standard will be obtained using Analyst software from Sciex Technologies (version 1.7.1). The Core lab will provide and set up LC-MRM-MS instrumentation. The applicant will prepare the plasma and urine samples for analysis in [name] lab and retrieve and analyze the LC-MRM-MS data generated at the Core Lab to obtain concentrations of each withanolide in each sample. The applicant will work with [name] to obtain PK curves and parameters.

L.2. Safety analysis (Aim 2)

Changes in laboratory outcomes from the baseline visit to the four-week follow-up visit for each study period will be presented using descriptive statistics (e.g., means and standard deviations, frequency and percent). Within group differences for laboratory outcomes at each dose will be evaluated for significance using paired t tests. Data will also be presented visually using histograms and line graphs. Treatment-emergent AEs will be organized by body system and summarized in table format by dose, with AE severity and possible relation to study drug reported.

L.3. Feasibility analysis (Aim 3)

The feasibility of administering REDCap surveys will be assessed by calculating the percentage of administered questionnaires that are returned and fully completed by participants, with feasibility defined as at least 80% of all administered questionnaires returned and completed. For each of the four timepoints (prior to PK Visit 1 and 2, prior to 4-Week Follow-Up Visit 1 and 2), the percentage of administered questionnaires returned and the percentage of returned questionnaires that are fully completed will also be reported.

L.4. Sample size

Based on a paired sample t-test with $\alpha=0.05$ and a sample size of 10 (anticipating two dropouts), we will have 95% power to detect an effect size of 1.3 (Cohen's d). Based on plasma levels of withaferin A, withanoside IV, and withanolide A observed in an unpublished PK study of 480 mg Shoden® in 16 healthy adults,⁷⁹ this effect size would be a difference in C_{\max} between the two doses of about 6.5 ng/ml for withaferin A, 2.2 ng/ml for withanoside IV, and 1.17 ng/ml for withanolide A. We expect to see much bigger differences between the two doses based on previous botanical studies where half doses resulted in C_{\max} values that were 35-50% lower than the full dose.⁸¹⁻⁸⁴

L.5. Data quality and management

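### L.2's only inference on laboratory safety is a paired t-test of mean change in 10 to 12 people, which has little power and fits isolated liver injury poorly

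*Combined protocol and SAP*

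**What the plan says.** Aim 2 (section B) hypothesises that a single administration and four weeks' use at 240 and 480 mg per day "will be well tolerated and produce no severe adverse events".

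L.2 is the analysis for that aim. Laboratory changes from the baseline visit to the four-week visit of each period "will be presented using descriptive statistics (e.g., means and standard deviations, frequency and percent", with histograms and line graphs. The one inferential sentence is: "Within group differences for laboratory outcomes at each dose will be evaluated for significance using paired t tests". Treatment-emergent adverse events are to be "summarized in table format by dose, with AE severity and possible relation to study drug reported". L.1 sets the level for testing: "All final statistical tests will be two-tailed and considered significant at" 0.05. L.2 gives no margin, confidence interval, abnormality threshold or shift table for the laboratory values.

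Three other places bear on this. C.2.3 names the hazard: "Isolated cases of mild to severe liver toxicity have occurred". Inclusion criterion 7 in F.2.2 requires "Hepatic (ALT, AST, bilirubin), renal (creatinine, estimated GFR), and TSH parameters within normal range", so every participant enters in range on these analytes. I.4.1 schedules a repeat comprehensive metabolic panel (CMP) 10 hours after each single dose to look at kidney and liver function.

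**The concern.** A test of mean change asks whether the group moved. The hazard in C.2.3 is that a few individuals move a long way. A large rise in one person increases the SD along with the mean, so the t statistic barely responds to how severe the rise is. With 10 to 12 people the test also has little power against a moderate shift of the whole group. A non-significant result is therefore expected in several situations that nobody would call safe.

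The descriptive part of L.2 could fill the gap, but frequency and percent need a category to count and none is defined. The laboratory-change analysis runs only from baseline to week 4, so the one routinely scheduled panel after a single dose, at 10 hours, is not in it.

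At stake is what the trial can say about tolerability. By C.2.3's own account, experience with 480 mg is a single administration in 16 participants. Section P expects the tolerability data to feed directly into later trials. A table of non-significant p-values could be taken for reassurance that it cannot give.

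**Working it through.** **Inputs.** n = 12 enrolled and 10 expected to complete (F.2.1); paired t-test (L.2); two-sided level 0.05 (L.1). The documents give no laboratory SD, so 0.5 SD below is an assumption.

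**The plan's own figure.** L.4 states 95% power at d = 1.3 with n = 10, for the pharmacokinetic comparison. Power is P(|T| > t_crit), with T noncentral t on n−1 df and noncentrality d√n. Here 1.3 × √10 = 4.11 and t_crit = 2.262, giving 95.4%. The figure reproduces, and the same formula is used next. L.4 gives no power for laboratory outcomes.

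**Step 1: a shift in the mean of 0.5 SD of the paired change.**
- n = 10: noncentrality 0.5 × √10 = 1.58, power 29.3%, miss rate 70.7%.
- n = 12: noncentrality 0.5 × √12 = 1.73, t_crit = 2.201, power 35.3%, miss rate 64.7%.
- 80% power needs a shift of 1.00 SD (n = 10) or 0.89 SD (n = 12).

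If 0.5 SD is instead read as the between-person SD, the standardised change is 0.5/√(2(1−ρ)), where ρ is the baseline-to-week-4 correlation (also assumed). The miss rates (n = 12 to n = 10) are then 73–78% at ρ = 0.3, 65–71% at 0.5, 47–55% at 0.7, 30–39% at 0.8 and 6–12% at 0.9.

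**Step 2: k people rise by the same amount L, the rest do not change.** The mean is kL/n and the variance is L²k(n−k)/(n(n−1)). So t = √(k(n−1)/(n−k)), and L cancels.

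| k | t, p (n = 10) | t, p (n = 12) |
|---|---|---|
| 1 | 1.00, 0.34 | 1.00, 0.34 |
| 2 | 1.50, 0.17 | 1.48, 0.17 |
| 3 | 1.96, 0.081 | 1.91, 0.082 |
| 4 | 2.45, 0.037 | 2.35, 0.039 |

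Unequal rises lower t: three rises of 200, 300 and 500 give p = 0.11.

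**Step 3: relax the assumption that the others do not change.** In simulation (100,000 runs), rises are expressed in SDs of the other participants' change.
- No background shift, rises of 10 SDs: p < 0.05 in under 0.1% of runs for k = 1, in 0.3% (n = 10) and 0.5% (n = 12) for k = 2, and in 9% and 10% for k = 3.
- No background shift, k = 3: 18% at 5 SDs and about 1% at 20 SDs.
- Background shift of 1 SD in the others, k = 1, n = 12: 82%, 39% and 0.1% for rises of 5, 10 and 20 SDs. The worse the single case, the less often the test rejects.
- Fixed values: three rises of 200 with everyone else up 10 give p = 0.046 (n = 10) and 0.041 (n = 12). Two rises of 200 with everyone else up 20 give 0.045 and 0.031.

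**Step 4: what a count could show.** With 0 events in n people, the one-sided 95% upper bound is 1 − 0.05^(1/n), which is 26% for n = 10 and 22% for n = 12. The two-sided Clopper-Pearson upper bound is 1 − 0.025^(1/n), which is 31% and 26%.

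**The case against.** The strongest reply is that the t-test is not the plan's safety criterion. The Aim 2 hypothesis is about tolerability and severe adverse events, and L.2 nowhere says that a non-significant change will count as evidence of safety. L.2 also plans frequencies, plots and adverse event tables by severity. Section N treats laboratory tests as a source of adverse events, follows up values outside the normal range and grades events by CTCAE. H.3 lists clinically significant laboratory change as a reason to discontinue, and two terminations for related serious events stop the study. In a 12-person pharmacokinetic pilot, low power for laboratory means is unavoidable.

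Most of this stands. A reader might infer that laboratory safety is judged by the t-test alone, or that severe injury in one to three people would pass unnoticed. The documents support neither: with so few participants, the displays and individual follow-up would probably show such a case. A reader might also infer from the step 2 table that the test can never reject with three or fewer cases. Step 3 shows that it can, when rises are smaller or the others also change.

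Three things remain. Clinical follow-up protects participants but is not an analysis rule, and the route from an abnormal value to the adverse event table is loose: N.1 frames attribution around symptoms. K.3 says no laboratory assessments after screening have clinical implications and no results will be shared, while section N says out-of-range results will be notified; those passages must be reconciled. And someone withdrawn for a laboratory change without a week-4 sample would drop out of the paired comparison, and L.2 does not say how that person is then counted.

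**Conclusion.** The point holds as a mismatch between the chosen inference and the safety question. It does not show that harm would go undetected.

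The paired t-test misses a shift of 0.5 SD of the paired change 71% (n = 10) or 65% (n = 12) of the time. Both figures rest on the assumed effect size and on that reading of the SD. For equal large rises with no change in the others, p is about 0.34, 0.17 and 0.08 for one, two and three people. Significance is then very unlikely with one or two cases and unlikely with three, though background change or smaller rises can produce it.

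The gap in the plan itself needs no assumption: L.2 defines no laboratory category to count, and its laboratory-change analysis leaves out the 10-hour CMP although Aim 2 covers single administration. An abnormal 10-hour value could still reach the adverse event table through section N. This is a cheap improvement.

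**What to change.** In L.2:

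1. For each dose, add a per-participant shift table for ALT, AST, bilirubin, creatinine/eGFR and TSH. It should run from the normal range required at entry to out of range, by the CTCAE grade that section N already adopts. Include all dosed participants and show missing week-4 values as missing. Use the 10-hour CMP for the CMP analytes and the week-4 laboratory results for all of them. Give each count an exact 95% upper bound and state whether it is one-sided or two-sided.
2. Report mean changes with 95% confidence intervals instead of p-values.
3. State that a non-significant mean change will not be taken as evidence of safety.

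The cost is a few sentences in L.2 and one table from data already collected. No visit, sample or clinical rule changes. The downside is a less favourable safety statement: intervals will be wide, and even no events at all leaves an upper bound between 22% and 31%, depending on n and on the type of bound. The change does not add power; it shows how little the sample can exclude.
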